5.5 Table or diagram summarising the chronology of the study

Actions	D0 (Baseline visit)	Every day (D1-28, discharge or death)	End of study: day 28 (+/- 4 days)
Information	X		
Informed consent	X		
Verification of inclusion and exclusion criteria	X		
History	X		
Clinical examination	X	X	X (if still hospitalized)
Clinical status on a seven-category ordinary scale	X	X	X
Tests (biochemistry, hematology, etc.)	X	X (at physician's discretion)	X (if still hospitalized)
Dispensation of treatments	X	X	X (if still hospitalized)
Compliance	X	X	X

Adverse events	X	X	X (by phone call if patients already discharged)
----------------	---	---	--

5.6 Distinction between standard care and study

TABLE: "Standard care" vs. "additional interventions" required specifically for the study

Interventions, procedures and treatments carried out for research purposes	Interventions, procedures and treatments associated with standard care	Interventions, procedures and treatments added for research purposes
Treatments	RAS blockers continuation, calcium channel blockers or other antihypertensive drugs, diuretics, nitrates antibiotics, remdesivir, lopinavir-ritonavir, tocilizumab, azithromycin, chloroquine, hydroxychloroquine	RAS blocker discontinuation
Visits	Daily visit during hospitalization	Phone call at day 28
Blood samples	complete blood count, creatinine, blood urea nitrogen, potassium, sodium, bicarbonate, alanine/aspartate aminotransferase, bilirubin, albumin, lactate dehydrogenase, prothrombin time, activated partial thromboplastin time, D-dimers, troponin I us, creatine kinase, natriuretic peptides (BNP or Nt-proBNP), C-reactive protein, procalcitonin, ferritin, arterial blood gas with lactate, viral load of SARS Cov 2 (blood)	None
Imaging	Chest X-ray, CT-chest, echocardiography or cardiac MRI if indicated	None

6 ELIGIBILITY CRITERIA

"ACORES2" protocol, version 1-3 of 07/04/2020

25/59

6.1 Inclusion criteria

1. Age \geq 18 year/old
2. Chronically treated with RAS blockers: ACE inhibitors or ARBs on the last prescription prior to admission and treatment duration \geq 1 month
3. Diagnosis of COVID-19, confirmed by the presence of SARS-CoV2 on any biological sample with any detection method
4. Patients hospitalized
5. Negative pregnancy test at inclusion visit for women of childbearing potential
6. Women of childbearing potential must agree to use adequate contraception according to Recommendations related to contraception and pregnancy testing in clinical trials, by Clinical Trial Facilitation Group (CTFG)

6.2 Exclusion criteria

1. Shock requiring vasoactive agents
2. Acute respiratory distress syndrome requiring invasive mechanical ventilation
3. Circulatory assistance
4. History of malignant hypertension according to the definition of the 2018 ESC/ESH guidelines on hypertension : severe hypertension associated with fundoscopic changes (flame hemorrhages and/or papilledema), microangiopathy, and disseminated intravascular coagulation (47)
5. Uncontrolled blood pressure despite the use of five antihypertensive drugs
6. History of nephrotic syndrome
7. History of hospitalization for hemorrhagic stroke in the past 3 months
8. RAS blockers therapy previously stopped $>$ 48h
9. Pregnancy, breastfeeding
10. No affiliation to the French Health Care System "Sécurité Sociale"
11. Inability to obtain informed consent

6.3 Recruitment procedure

Patients will be recruited in hospitalization.

Considering the high number of patients infected with SARS-CoV2 in Italy, we believe that the number of patients infected with SARS-CoV2 in France can be similar and that enrolling 554 patients in 12 centers is highly feasible (47 patients/months/center).

	Number of participants
Total number of participants to be included	554
Number of centers	12

Enrolment period (months)	1
Number of participants/centre	47
Number of participants/centre/month	47

6.4 Termination rules

6.4.1 Criteria and procedures for prematurely terminating the study treatment

Several situations are possible

- Temporary suspension of treatment: the investigator must document the reason for suspending and resuming the treatment in the participant's source file and the case report form (CRF)
- Premature discontinuation of treatment, but the participant remains enrolled in the study until the end of their participation
- Premature discontinuation of treatment and withdrawal from the study

The investigator must:

- Document the reason(s)
- Collect the assessment criteria at the time of ending participation in the study, if the participant agrees
- Schedule a follow-up for the participant, particularly in case of a serious adverse event.

In the case of severe adverse events, the investigator must notify the sponsor and follow up the participant for 28 days \pm 4 days. Notification of a serious adverse event must be sent by email ([contact]) to the sponsor. The serious adverse event will be monitored until it is resolved. As a Data Safety Monitoring Board has been created, the committee can specify and/or validate the follow-up methods.

6.4.2 Criteria and procedure for premature withdrawal of a participant from the study

- Participants may exit the study at any time and for any reason.
- If, during the course of his/her participation in the study, the participant presents one of the following exclusion criteria, then the study product/procedure must be discontinued but the participant will continue to be monitored for the study.
- The investigator can permanently withdraw a participant from the study in case of consent withdrawal.
- Participant lost to follow-up: the participant cannot be located. The investigator must make every effort to reconnect with the participant (and document his attempts in the source file), at least to determine whether the participant is alive or dead

If a participant withdraws consent, any data collected prior to the date of premature exit may still be used.

"ACORES2" protocol, version 1-3 of 07/04/2020

27/59

- If a participant exits the study prematurely, and if the participant agrees, state the procedure and schedule for collecting the data required by the protocol (primary endpoint, secondary endpoints, safety assessment)
- In case of withdrawal consent, patient's care will be done according to investigator decision.
- In case of serious adverse events, see the corresponding section on vigilance

6.4.3 Follow-up of participants following premature withdrawal from the study

If a participant discontinues the study, this will in no way affect their usual care for their condition.

6.4.4 Full or partial discontinuation of the study

AP-HP as sponsor or the Competent Authority (ANSM) can prematurely discontinue all or part of the study, temporarily or permanently, in the following situations:

- first of all, if suspected unexpected serious adverse reactions (SUSARs) are observed in one of the treatment arms if there is a discrepancy in the serious adverse reactions between the treatment arms, requiring a reassessment of the benefit-risk ratio for the study.
- if an interim analysis confirms the efficacy of one of the treatment arms or, alternatively, the lack of efficacy.

Similarly, AP-HP, as the sponsor, or the Competent Authority (ANSM) may decide to prematurely discontinue the study due to unforeseen issues or new information about the product, in light of which the objectives of the study or clinical programme are unlikely to be achieved.

AP-HP as sponsor reserves the right to permanently suspend enrolment at any time if it appears that the inclusion objectives are not met.

If the study is prematurely discontinued for safety reasons, the decision and justification will be provided by the sponsor (AP-HP) to the Competent Authority (ANSM) and to the CPP (Research Ethics Committee) within a period of 15 days.

7 TREATMENT ADMINISTERED TO STUDY PARTICIPANTS

This study is a study without any added treatment.

Patients included in the study are already chronically treated by a RAS blockers.

The ACORES-2 trial will stop RAS blockers in one arm of the patients.

Therefore, there is no administrated treatment in this research.

7.1 Description of the experimental group

The experimental group, including 277 COVID-19 patients with chronic RAS blockers treatment will undergo withdrawal of their RAS blockers treatment. The treatment discontinuation will be tracked into the patient file.*

7.2 Description of the non-experimental group

The non-experimental group, including 277 COVID-19 patients with chronic RAS blockers treatment will continue their usual RAS blockers treatment without modification. Prescription of intakes will be kept into the patient file.*

*With respect to the epidemic context, all traceability will be insured with current care patient documents

7.3 Authorized and prohibited treatments (medicinal, additional medicinal, surgical), including rescue medications

Treatments interacting with the renin-angiotension system (other ACE inhibitors or ARBs than the usual patients' treatment) are prohibited.

- For all patients randomized in the discontinuation group, an alternative treatment will be proposed according to the appropriate guidelines of the European Society of Cardiology (hypertension, heart failure, coronary artery disease) and the tolerance of the patient
- In particular :
- in individuals at risk of uncontrolled blood pressure: consider Calcium Channel blocker as a first line option, if necessary other antihypertensive drug (non-RAS blockers) can be added according to the physician decision
- In individuals with history of heart failure: consider adding diuretics and nitrates (oral or IV according to the physician decision)

Other drugs indicated for heart failure or hypertension such as calcium channel blockers, diuretics, beta blockers, central acting agents, nitrates are authorized with medical prescription.

Specific clinical (e.g.: blood pressure/Signs of heart failure) or biological (e.g.: creatinin, electrolytes), follow-up for each drug used as a replacement therapy in the group "discontinuation" will be performed according to the drug registration notice (RCP) of each drug

For woman of childbearing age, initiation or following of a contraception is needed to be included in the study.

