	
Consecutive patients with a diagnosis of COVID-19 confirmed by the presence of SARS-CoV-2 on any biological sample with any detection method requiring hospitalization will be enrolled.
 
Patients will be randomly assigned in a 1:1 ratio to continue (group continuation) or not (group discontinuation) their usual RAS blockers therapy plus standard of care (oxygen, noninvasive or invasive ventilation, antibiotics, vasopressor support, renal-replacement therapy, circulatory assistance if needed). The randomization will be stratified on the indication of RAS blockers (heart failure vs. other indication).
 
If the patients' usual treatment is not available in the hospital, a switch to ramipril for ACE inhibitors or valsartan for ARBs will be done in the continuation group or in case of cross-over.
 
Written information consent will be obtained from all patients.
 
All the medical data and outcomes will be record prospectively.
 
A phone call will be done at day 28 (\pm 4 days) for all survivor's patients.

Population of study participants	Adult patients with a diagnosis of COVID-19 requiring hospitalization and on prior therapy with RAS blockers.
Inclusion criteria	
Subjects meeting all of the following criteria will be considered for enrolment into the study:
 
 1. Age \geq 18 year/old 2. Chronically treated with RAS blockers (ACE inhibitors or ARBs on the last prescription prior to admission with a treatment duration \geq 1 month) 3. Diagnosis of COVID-19 confirmed by the presence of SARS-CoV-2 on any biological sample with any detection method 4. Patients hospitalized 5. Negative pregnancy test at inclusion visit for women of childbearing potential 6. Women of childbearing potential must agree to use adequate contraception according to Recommendations related to contraception and pregnancy testing in clinical trials, by Clinical Trial Facilitation Group (CTFG)
Exclusion criteria	
Subjects presenting with any of the following will not be included in the study:
 
 1. Shock requiring vasoactive agents

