2.5 Identification and description of the investigational medication or medications

The ACORES-2 trial does not involve the use of an experimental medication (usual RAS blockers).

All the patients included in the ACORES-2 trial are already taking RAS blockers before participating in the research.

The experimental arm is therefore the discontinuation of this therapy.

2.6 Description and justification of the dosage, route of administration, administration schedule and treatment duration

The dosage will be the usual patient's one. In the continuation group, the treatment will be continued

RAS blockers are given according to the standard of care and the choice of the prescribed RAS blocker (INN and dosage) are unrelated to their participation in the research.

- For all patients randomized in the discontinuation group, an alternative treatment will be proposed according to the appropriate guidelines of the European Society of Cardiology (hypertension, heart failure, coronary artery disease) and the tolerance of the patient

In particular :

- in individuals at risk of uncontrolled blood pressure: consider Calcium Channel blocker as a first line option, if necessary other antihypertensive drug (non-RAS blockers) can be added according to the physician decision
- In individuals with history of heart failure: consider adding diuretics and nitrates (oral or IV according to the physician decision)

2.7 Summary of the known and foreseeable benefits and risks for the research participants

The potentials benefits of discontinuation of RAS blockers for the participants are the following:

- Reduction of the risk of developing severe forms of COVID-19 by reducing the synthesis of ACE2 and the infection of patient's cells by the SARS-CoV-2
- Reduce the delay to recovery and hospital discharge
- Reduction of hypotension requiring vasopressors
- Reduction of the rate of acute kidney injury
- Better knowledge of the impact of RAS blockers on the acute lung injury related to coronaviruses.
- Better knowledge of the impact of RAS blockers withdrawal in cardiovascular high-risk patients

The potentials risk of discontinuation of RAS blockers for the participants are the following:

- Increase of cardiovascular events, such as acute heart failure, uncontrolled hypertension, myocardial infarction or stroke
- Increase of COVID-19 related acute lung injuries by reducing the synthesis of ACE2 and angiotensin(1-7)

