4.2.4 Randomization

Randomization will be performed with IWRS (Cleanweb).

[figure not shown]
URC Lariboisière Saint-Louis will be done randomization list according to AP-HP Standard Operating Procedures (SOP).

Patients fulfilling the inclusion criteria and without any exclusion criteria that agree to enter the protocol and have signed the inform consent form during the consultation (inclusion) will be randomized in a 1:1 ratio to:

- Group Discontinuation = discontinuation of RAS blocker therapy until the end of the study which correspond to day 28 (experimental arm). After day 28, RAS blockers could be reintroduced or not, according to the physician decision.
or
- Group Continuation = continuation of RAS blocker therapy (control arm)

The randomization will be stratified on the indication of RAS blockers (heart failure vs. other indication).

Inclusion and randomization will be done the same day.

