12.3 Planned Analyses

12.3.1 Populations to be analysed

The main analysis will be based on the intent-to-treat population (ITT) of all patients randomised (irrespective of which study treatment is given or if any study treatment is adequately received). Per protocol analysis (PP) of all patients randomized & treated without major protocol violations/deviations will be considered as secondary.

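### The Summary orders a switch to ramipril or valsartan when the usual RAS blocker is unavailable, sections 7.2 and 7.3 rule it out, and so the compliance and per-protocol status of a switched patient is unsettled

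*Protocol*

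**What the plan says.** The Summary, under the design of the study, sets a condition and an instruction. The condition is "If the patients' usual treatment is not available in the hospital". The instruction is that "a switch to ramipril for ACE inhibitors or valsartan for ARBs will be done in the continuation group or in case of cross-over". It is worded as something that will happen, not as an option, and it appears nowhere else in the protocol.

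The body of the protocol reads differently:

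- Section 7.2 says that control patients "will continue their usual RAS blockers treatment without modification".
- Section 7.3, on authorized and prohibited treatments, says of agents acting on the renin-angiotensin system that "other ACE inhibitors or ARBs than the usual patients' treatment) are prohibited". It gives no exception and does not refer back to the Summary.
- Section 2.6 says that "The dosage will be the usual patient's one" and that "the choice of the prescribed RAS blocker (INN and dosage) are unrelated to their participation in the research". It does not mention substitution.
- Section 4.2.4 describes the control arm by type of treatment, not by product: "Group Continuation = continuation of RAS blocker therapy (control arm".
- Section 12.3.1 makes intention-to-treat the main analysis, "irrespective of which study treatment is given or if any study treatment is adequately received". The per-protocol analysis is secondary and keeps patients who were treated without major violations or deviations.

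**The concern.** Continuing versus stopping a RAS blocker is the whole intervention, so the rule for keeping a control patient on treatment is an operative one. Here the same act is ordered in one place and prohibited in another.

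Two things are at stake. The first is classification. A control switched to ramipril or valsartan follows the Summary and breaches section 7.3, so two analysts could place that patient differently in the per-protocol set and each cite the protocol. Cross-overs apart, any such exclusions would all come from the control arm. The second is conduct. A site that takes section 7.3 at its word has no permitted RAS blocker for a control whose usual product cannot be had. That patient could end up untreated and so resemble the discontinuation arm.

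**Working it through.** No arithmetic applies: the protocol gives no figure that bears on this point, and resolving it changes no stated sample size, significance level or power. The check sets the texts side by side for each situation a site can meet.

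| Situation | Summary | Section 7.2 | Section 7.3 | Section 4.2.4 |
|---|---|---|---|---|
| Control, usual product available and continued | complies | complies | complies | complies |
| Control, product unavailable, switched to ramipril or valsartan | complies | breaches | breaches | complies |
| Control, product unavailable, given no RAS blocker | breaches | breaches | complies | breaches |
| Cross-over from discontinuation, product unavailable, given the substitute | complies | does not apply | breaches | does not settle it |

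1. The first row shows that the texts agree whenever the usual product can be had. The conflict is confined to the condition named in the Summary.
2. In the second and third rows no course satisfies every column. Switching breaks 7.2 and 7.3. Not switching breaks the Summary and 7.2, and takes the patient off the therapy that section 4.2.4 assigns.
3. The last row shows that 7.3 also catches cross-overs, whom the Summary names explicitly. Their per-protocol status may in any case be decided by the cross-over itself, so for them the conflict is mainly one of treatment rules.
4. Section 2.6 is in tension with the switch rather than in flat contradiction. It ties the dosage to the patient's usual one without saying what applies after a substitution. It also says that drug and dosage do not depend on trial participation, whereas the Summary names specific substitutes.
5. For section 12.3.1, read the second row twice. Taken from the Summary, the patient was treated as planned and stays in the per-protocol set. Taken from 7.3, the patient received a prohibited drug and is a candidate for exclusion. Which deviations count as major is normally left to the SAP. The SAP cannot settle whether this is a deviation at all while the protocol both orders and prohibits it.
6. Section 13.4 requires events arising from non-compliance with the protocol to be declared to the sponsor. For these patients that duty has no consistent reference point.
7. On size, the protocol does not say how often a usual product would be unavailable. The number affected could lie anywhere from none to many of the 277 controls, plus any cross-overs.

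**The case against.** The best defence is that the Summary is the only text addressing unavailability, so it can be read as a specific provision beside a general prohibition. On that reading section 7.3 is aimed at adding a second RAS blocker, or at one slipping into the discontinuation arm. That is plausible as intent, but neither reading is written down. Even if 7.3 is narrowed this way, the requirement in 7.2 that controls stay on their own drug unchanged still conflicts with a change of product.

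The defence does succeed against three stronger conclusions that a reader might draw:

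- That exposure in the control arm is undefined. It is not. Section 4.2.4 and the comparator entry in the Summary define it as staying on a RAS blocker, and the switch stays within class (ACE inhibitor to ramipril, ARB to valsartan).
- That the per-protocol set is undefined. Section 12.3.1 defines it in general terms. Only the status of switched patients is open, and the absence of a list of major deviations from the protocol is no fault.
- That the primary analysis loses a calculable amount of power. Intention-to-treat membership does not depend on treatment received, and a within-class switch leaves the patient on a RAS blocker. Dilution would require sites to set aside the Summary and leave controls untreated. The protocol states neither the share of patients who might be affected nor an expected number of events, so no power figure can be derived from it.

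**Conclusion.** The contradiction stands as written in current text. A patient whose usual RAS blocker is unavailable cannot be managed in a way that complies with the Summary, section 7.2 and section 7.3 together. Whether a switched patient counts as compliant, and so belongs in the per-protocol set, depends on which section is read.

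The certain consequence is limited to the conduct rule for these patients and to a secondary analysis. Narrowing of the between-arm contrast in the primary analysis is possible, but only if some sites follow 7.3 literally and leave controls without the drug. The protocol does not tell them to do so, and it does not allow the effect to be sized. The conclusion rests on the wording alone and assumes only that some patients' usual product will be unavailable, which the Summary itself anticipates. It should be corrected because it concerns an operative treatment rule and is cheap to put right.

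**What to change.** Reconcile the Summary with sections 2.6, 7.2 and 7.3 so that sites and pharmacies read one rule for the patient whose usual product is unavailable, covering both controls and cross-overs. Which rule that should be is a clinical choice for the investigators and the sponsor. When the per-protocol set is built under section 12.3.1, classify any substitution consistently with the reconciled rule, in the same way at all sites. Sections 5.2 and 5.5 already provide for recording cross-over and compliance, so it is enough to check that those records identify a substitution.

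The cost is a few lines of wording in four places and one line for the per-protocol classification. The sample size, the endpoints and the primary analysis do not change. With enrolment planned to last one month, the change is useful only if it is made before or very early in recruitment.
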